7.1.3 Suspected Unexpected Serious Adverse Reactions

A suspected unexpected serious adverse reaction (SUSAR) is defined as an untoward and unintended response to a study drug, which is not listed is the applicable product information (eg, IB for an unapproved IMP or the SmPC for an authorised medicinal product), and meets one of the following serious criteria: results in death, is life-threatening, requires hospitalisation or prolongation of an existing hospitalisation, results in persistent or significant disability or incapacity, or is a congenital anomaly or birth defect, or is an important medical event that may not result in death, be lifethreatening, or require hospitalisation; and is assessed as causally related to the IMP. For SUSARs, the blind will be broken for safety reporting purposes.

7.1.4 Clinical Laboratory Abnormalities and Other Abnormal Assessments

Laboratory abnormalities without clinical significance should not be recorded as AEs or SAEs. However, laboratory abnormalities as per the investigator's assessment (eg, clinical chemistry, haematology, and urinalysis abnormalities) that require medical or surgical intervention or lead to IMP interruption, modification, or discontinuation must be recorded as an AE or SAE, as applicable. In addition, laboratory or other abnormal assessments (eg, in ECGs, X-rays, or vital signs) that are associated with signs and/or symptoms must be recorded as an AE or SAE if they meet the definition of an AE or SAE as described in Sections 7.1 and 7.1.2. Any worsening of existing abnormalities that are associated with signs and/or symptoms (except for SCCHN-related pre-existing conditions, including disease progression [see Section 7.3]) should be reported as AEs or SAEs, as appropriate. If the laboratory abnormality is part of a syndrome, record the syndrome or diagnosis (eg, anaemia), not the laboratory result (ie, decreased haemoglobin).

For specific information on handling of clinical laboratory abnormalities, see Section 5.3.2.

7.1.5 Adverse Events of Special Interest

The AESIs for this study are anaemia and hypothyroidism.

AESIs of anaemia will be defined as CTCAE Grade ≥ 3 anaemia. Please refer to Section 5.3.2.1 for details regarding the detection and management of potential cases of anaemia.

AESIs of hypothyroidism will be defined as TSH levels of ≥ 10 mIU/L. AESI will be unconfirmed with only one test. Please refer to Section 5.3.2.2 for details regarding the detection and management of hypothyroidism.

The AESI should be reported by the investigative site to the ICON Drug Safety Centre within 24 hours of learning about the event by completing the paper safety report form and sending it via email or fax. The documentation and processing of AESIs is further detailed in the investigator site file.

Investigators will indicate on the relevant Adverse Event eCRF page if the event meets the criteria for an AESI.

7.2 Assessment of Adverse Events

7.2.1 Severity

The terms serious and severe are not synonymous. The general term "severe" is often used to describe the intensity (severity) of a specific event; the event itself, however, may be of relatively minor medical significance (such as a Grade 3 headache). This is NOT the same as serious, which is usually associated with events that pose a threat to a patient's life or ability to function (see Section 7.1.2). A severe AE (classified as Grade 3) does not necessarily need to be considered serious. For example, a WBC count of 1000/mm³ to less than 2000/mm³ is considered Grade 3 (severe) but may not be considered serious. Seriousness (not intensity) serves as a guide for defining regulatory reporting obligations.

Investigators will grade all AEs by severity using CTCAE (Version 5.0).

If an AE is not listed in the CTCAE criteria, a corresponding grading is to be performed by the investigator based on his/her best medical judgment as follows:

- Mild (Grade 1): asymptomatic or mild symptoms; clinical or diagnostic observations only; intervention not indicated
- Moderate (Grade 2): minimal, local, or noninvasive intervention indicated; limited age-appropriate instrumental activities of daily living (ADL)
- Severe (Grade 3): medically significant but not immediately life-threatening; hospitalisation or prolongation of hospitalisation indicated; disabling; or limiting self-care ADL
- Life-threatening (Grade 4): life-threatening consequences; urgent intervention indicated
- Death (Grade 5): death related to an AE

7.2.2 Causality

Investigators are required to systematically assess the causal relationship between the AEs and SAEs and the exposure to the IMP using the following definitions:

Related:

- The AE has a reasonable possibility of an association with the IMP because:
 - The AE follows a reasonable temporal sequence to IMP administration, and cannot be reasonably explained by the patient's clinical state or other risk factors (eg, disease under study, concurrent diseases, or concomitant medications).
 - The AE follows a reasonable temporal sequence to IMP administration, and it is a known reaction to the drug under study or a related chemical group or is predicted by known pharmacology or nonclinical safety.

Not Related:

• The AE does not follow a reasonable sequence from IMP administration, or it can be reasonably explained by the patient's clinical state or other risk factors (eg, disease under study, concurrent diseases, and concomitant medications).

7.3 Documenting and Reporting Adverse Events

Reporting of AEs will begin when the patient has provided informed consent and will continue up to the 28 days after the last IMP administration.

Occurrence of AEs may be volunteered spontaneously by the patient; discovered as a result of general, nonleading verbal questioning by the study staff; or determined by physical examination or other safety assessments. All AEs will be monitored and recorded in the eCRF throughout the entire study. Note that worsening of SCCHN-related pre-existing conditions, including disease progression, will not be reported as AEs. An event solely attributed to tumour progression should not be reported as an AE, unless the signs and symptoms of the event are more severe than expected for the patient's condition. If the criteria for an AE is not met, disease progression will be recorded as efficacy data. Worsening of other existing abnormalities that are associated with signs and/or symptoms should be reported as AEs (or SAEs), as appropriate. Any event that meets one or more of the seriousness criteria will be reported as an SAE per the procedures outlined in Section 7.4.

For all AEs, the investigator must pursue and obtain adequate information (a description of the event, severity, time of occurrence, including whether the AE onset was before, during, or after the IMP administration if the AE started on a dosing day, duration, and any action, eg, treatment/follow-up tests). The outcome of the event should be provided along with the investigator's assessment of the relationship to the IMP. The investigator must also assess whether the event meets the criteria for classification as an SAE.

It is the investigator's responsibility to review all documentation (eg, hospital notes, laboratory reports, and diagnostic reports) related to an AE. Wherever possible, the investigator's diagnosis, not the individual signs and symptoms, will be documented as the AE.

Investigators are not obligated to actively seek AEs or unrelated SAEs after the patient's conclusion of study participation. However, if the investigator learns of any SAE, including death, at any time after a patient has been discharged from the study, and he/she considers the event to be reasonably related to the IMP or study participation, the investigator must promptly notify the sponsor. The investigator is expected to follow a potentially related SAE until it has resolved, it has resolved with sequelae, or the patient is lost to follow-up.

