In addition, for patients with a suitable archival tumour biopsy sample available, the archival sample may be used to assess CAFs level and determine eligibility (Note: this can only be performed after the patient has provided signed informed consent). This will not dispense from the need for a recent pre-study tumour biopsy, collected during or within 30 days prior to the Screening Period, for patients eligible for the study.

To be considered suitable for determination of CAF levels, archival biopsy must have been collected within 6 months prior to the Screening Visit (Visit 1), and the patient must

have received no further anti-cancer therapy since then (see Section 5.2.2 for more details on suitability). Elevated CAF levels in suitable archival tumour tissue will meet the eligibility requirement based on CAF levels, but an additional pre-study biopsy (during or within 30 days of the Screening Period) is needed for reliable Baseline biomarker analysis.

Eligible patients will be randomised to the investigational medicinal product (IMP) setanaxib 800 mg BID, or placebo, according to a 1:1 randomisation ratio, stratified by HPV status. See Section 6.3 for further details on the method of assigning patients to the treatment groups, and see Section 6.4 for further details on the dose and administration of setanaxib and placebo. Treatment with pembrolizumab will be initiated on the same day (Day 1) as the first dose of IMP, and will be administered according to current clinical guidelines and labelling, ie, 200-mg intravenous (IV) infusion q3w. See Section 6.7 for further details on the dose and administration of pembrolizumab.

Treatment with pembrolizumab will continue until: RECIST v1.1-defined disease progression as determined by the investigator (Eisenhauer et al 2009), unacceptable toxicity, or a maximum of 24 months. If progression is suspected, but not confirmed, study treatment may continue until confirmation of radiological progression.

Treatment with setanaxib or placebo will continue throughout the period of pembrolizumab therapy. When pembrolizumab is discontinued, blinded study treatment will be discontinued at the same time.

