Baseline assessments will be performed on Day 1 (Visit 2). Post-Baseline assessments will be performed every 3 weeks up to pembrolizumab discontinuation. Following permanent IMP discontinuation at any time during the study, patients will undergo an End-of-Treatment (EoT) Visit as soon as possible and a Safety Follow-up Visit at 28 days after the last dose. Tumour assessments will be conducted from the date of randomisation and continue until RECIST v1.1-defined disease progression, irrespective of treatment discontinuation. Efficacy Follow-up for PFS and survival will continue until at least 38 progression events have occurred. AEs will be recorded up to 28 days after study treatment discontinuation, while any further anti-cancer medication will be recorded until disease progression.

Throughout the study, particular attention will be given to the detection and management of potential cases of anaemia (see Section 5.3.2.1), and potential cases of hypothyroidism (see Section 5.3.2.2).

Safety and tolerability data will be regularly reviewed by an unblinded IDMC, with the first assessment after approximately 12 patients (6 per treatment group) have had the opportunity to complete at least 1 cycle of pembrolizumab +/- setanaxib, followed by periodic assessments at a frequency defined in the IDMC Charter (see Section 9.4). The IDMC may recommend change(s) to the setanaxib dose regimen or study conduct based

on the safety data reviews, as defined in the IDMC Charter. The role and responsibilities of the IDMC will be outlined in the IDMC Charter.

After approximately 12 patients (6 per treatment group) have completed their Baseline and post-treatment biopsy, initial gene expression and biomarker data in tumour tissue may be reviewed by the sponsor, who will remain masked to randomised treatment assignment. A second review may be performed, if required.

The investigator, site personnel, the sponsor and their representatives involved in monitoring and conducting the study, and the patients will be blinded to the IMP administered. See Section 6.2 for details on access to the treatment codes in the event of emergency unblinding.

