5.3.3 Pregnancy

All patients are required to meet the requirements relating to pregnancy and use of contraception described in the inclusion and exclusion criteria (see Section 4.1 and Section 4.2, respectively). Male and female patients of childbearing potential must receive pregnancy prevention counselling and be advised of the risk to the foetus if they become pregnant or father a child during treatment and for 6 months after the last dose of IMP or pembrolizumab, whichever is the later. Additional medications given during the study may alter the contraceptive requirements. These additional medications may require female patients to use highly effective methods of contraception and/or for an increased length of time. In addition, male patients are also required to use contraception. The investigator must discuss these contraceptive changes with the patient.

For female patients who are considered postmenopausal but have less than 12 months of amenorrhea and who are not on concomitant oestrogen replacement therapy, a high FSH level in the postmenopausal range will be required at Screening. Confirmation with more than one FSH measurement is required.

Serum (beta human chorionic gonadotrophin) or urine pregnancy tests will be performed for female patients of childbearing potential at the time points indicated in Table 1.

Female patients of childbearing potential must have a serum pregnancy test at the Screening Visit. The blood sample for the serum pregnancy test must be taken within 7 days of Day 1. Therefore, if Screening Visit is performed more than 7 days prior to Day 1, the serum pregnancy test must be repeated within 7 days of Day 1. The result must be negative for the patient to be eligible for the study. If the test result is positive,

the patient must be excluded from the study. The serum pregnancy tests will be analysed by the central laboratory. A negative urine pregnancy test result is required at Baseline/Randomisation and at each visit before dosing. Urine pregnancy tests will be analysed locally.

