7.1.1 Adverse Events

An AE is any untoward medical occurrence in a patient or clinical study patient administered a pharmaceutical product and that does not necessarily have a causal relationship with this treatment. An AE can, therefore, be any unfavourable and unintended sign (including an abnormal laboratory finding), symptom, or disease temporally associated with the use of a medicinal (investigational) product, whether or not related to the medicinal (investigational) product.

AEs that occur, having been absent before the date and time of the first dose of the IMP, or having worsened in severity or seriousness after initiating the IMP until 28 days after the date and time of last dose of IMP, will be classified as TEAEs.

An event solely attributed to tumour progression should not be reported as an AE, unless the signs and symptoms of the event are more severe than expected for the patient's condition. If the criteria for an AE is not met, disease progression will be recorded as efficacy data. Any event that meets one or more of the seriousness criteria will be reported as an SAE per the procedures outlined in Section 7.4.

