10.10 Adverse Events

10.10.1 Treatment-Emergent Adverse Events

A treatment-emergent adverse event (TEAE) is an AE that occurs, having been absent before the first dose of IMP, or having worsened in severity or seriousness after the first dose of IMP, up to and including 28 days after the date and time of last dose of IMP.

Any AEs that occur 28 days after the date of the last dose of IMP will be considered a post-treatment AE and will be listed only.

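### The TEAE window closes 28 days after the last IMP dose even if pembrolizumab continues, and the protocol gives conflicting end points for AE collection

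*Protocol*

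**What the plan says.** **TEAE window.** Protocol 7.1.1 counts an AE as treatment-emergent "until 28 days after the date and time of last dose of IMP", and 8.4.6 repeats this. SAP 10.10.1 has "up to and including 28 days after the date and time of last dose of IMP" and makes anything later a post-treatment AE that appears in listings only.

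**AE collection.** Protocol 7.3 says reporting "will continue up to the 28 days after the last IMP administration". The next paragraph of 7.3 says "All AEs will be monitored and recorded in the eCRF throughout the entire study". Section 3.1 says "AEs will be recorded up to 28 days after study treatment discontinuation", as does Table 1 footnote r in substance.

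**Visits.** Section 3.1 says "Post-Baseline assessments will be performed every 3 weeks up to pembrolizumab discontinuation". Table 1 footnote a gives a patient who stops IMP early an EoT Visit and a visit 28 days after the last IMP dose. After that it mentions only efficacy assessments.

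**SAEs.** Section 7.4 and Table 1 footnote s limit reporting after the EoT Visit to SAEs considered related to IMP.

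**Link between the drugs.** Section 3.1 says "Treatment with pembrolizumab will continue until: RECIST v1.1-defined disease progression as determined by the investigator", unacceptable toxicity or 24 months, and that stopping pembrolizumab stops IMP. It says nothing about the reverse. Section 5.3.3 sets the pregnancy reporting period at "6 months after the last dose of IMP or pembrolizumab, whichever is the later".

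**The concern.** The safety objective compares setanaxib plus pembrolizumab with placebo plus pembrolizumab. Protocol 4.3.1, 5.3.2.1 and 5.3.2.2 provide for IMP to be stopped for good, for example for anaemia or hypothyroidism, without mentioning pembrolizumab. None of the pembrolizumab stopping reasons in Section 3.1 need be met at that point. Such a patient may still be on one half of the study regimen when the tabulation window shuts.

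Two things are at stake. First, sites reading different sections could stop recording AEs at different dates for the same kind of patient. Second, SAP 12.6.1 reports event counts and percentages of patients, with no adjustment for time observed. If IMP-only stops are more common in one arm, that arm's AE tables cover less pembrolizumab time, and late events are under-counted there relative to the other arm. Protocol Table 2 names thyroid disorder as the overlapping toxicity, and raised TSH is itself one of the triggers for stopping IMP, so a difference between arms is plausible. It is not established.

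**Working it through.** The plan gives no figure to reproduce. The check is a comparison of passages, then calendar arithmetic.

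**1. Passages side by side**

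| Place | What it governs | End point |
|---|---|---|
| Protocol 7.1.1, 8.4.6; SAP 10.10.1 | TEAE window | last IMP dose + 28 days |
| Protocol 7.3, first paragraph | AE reporting | last IMP dose + 28 days |
| Protocol 7.3, second paragraph | AE recording | whole study |
| Protocol 3.1; Table 1 footnote r | AE recording | study treatment discontinuation + 28 days |
| Protocol 3.1 | 3-weekly assessments | pembrolizumab discontinuation |
| Table 1 footnote a | visits after early IMP stop | last IMP dose + 28 days, then efficacy only |
| Protocol 7.4; Table 1 footnote s | SAEs of any cause | EoT Visit; afterwards IMP-related only |

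Study treatment is not defined. Section 3.1 uses it in the paragraph on continuing pembrolizumab, but uses blinded study treatment for IMP alone.

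**2. A patient off IMP and on pembrolizumab**

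The collection rows give at least three different end dates for this patient. The TEAE row gives one: whatever is collected, events after last IMP dose + 28 days stay out of every TEAE table in SAP 12.6.1 and 12.6.2, including the special-interest, serious and fatal ones. For SAEs, the EoT Visit follows IMP discontinuation as soon as possible, and 7.2.2 assesses causality against IMP only. Under 7.4, a serious event attributed to pembrolizumab that starts after that visit need not be reported.

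**3. How long the gap could be**

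Let I be the week IMP stops and P the week of the last pembrolizumab infusion.

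- Window closes at I + 4.
- Gap before the last infusion = max(0, P − (I + 4)).

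Table 1 schedules infusions every 3 weeks, the last at Week 102. Assuming the longest case, P = 102:

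| I (week) | Window closes | Gap (weeks) | Infusions after closure |
|---|---|---|---|
| 3 | 7 | 102 − 7 = 95 | Weeks 9 to 102: (102 − 9)/3 + 1 = 32 |
| 12 | 16 | 102 − 16 = 86 | Weeks 18 to 102: (102 − 18)/3 + 1 = 29 |
| 24 | 28 | 102 − 28 = 74 | Weeks 30 to 102: (102 − 30)/3 + 1 = 25 |
| 51 | 55 | 102 − 55 = 47 | Weeks 57 to 102: (102 − 57)/3 + 1 = 16 |

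These are near the maximum. Protocol 1.3 anticipates median dosing of 3 to 6 months. With I = 3 and P = 24 the gap is 24 − 7 = 17 weeks. If pembrolizumab stops with IMP, P − (I + 4) is negative and the gap is zero.

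**4. What cannot be computed**

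The documents do not give the number of IMP-only stops, the time on pembrolizumab afterwards, or any split by arm.

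**The case against.** A reader might infer that patients taken off IMP stop contributing safety data. The documents do not support that. Section 7.3 also calls for AE recording throughout the study, Section 3.1 keeps 3-weekly assessments going to pembrolizumab discontinuation, and 5.3.2.1 and 5.3.2.2 require at least weekly monitoring until haemoglobin or thyroid values return to Baseline. Later AEs that are collected are listed, IMP-related SAEs are still reported, and the laboratory summaries are not cut by the TEAE window. The table of weeks above is time outside the TEAE window under an assumed course, not time with no AE collection.

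A reader might also infer that the protocol expects pembrolizumab to outlast IMP, because 5.3.3 and the contraception criteria refer to the later of the two last doses. That wording covers either order. IMP is taken twice daily and pembrolizumab every 3 weeks, so the last IMP dose can be the later one when both stop together. The wording shows only that the two dates can differ.

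Nor is the event that triggers an IMP stop lost. Hypothyroidism that starts on IMP is already a TEAE and an AESI. Only later events are affected.

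Finally, an IMP-anchored TEAE table is defensible in itself: pembrolizumab is non-investigational background treatment (6.7), and causality is judged against IMP. That is a reason to keep such a table, but it does not resolve the conflicting collection rules. Nor does it make an IMP-only window sufficient for comparing two combination regimens.

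**Conclusion.** The point holds in a limited form. The IMP-only TEAE window is unambiguous in both documents. The end of AE collection is contradictory, and SAE reporting narrows to IMP-related events after the EoT Visit. How a patient off IMP but on pembrolizumab should be followed for safety is not defined.

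The size is conditional and unknown. It rests on pembrolizumab continuing after an IMP-only stop, which the documents permit by silence and do not state. Bias between arms also requires such stops, or the time on pembrolizumab after them, to differ by arm. Nothing in the documents shows that they do, or in which direction. With about 25 patients per arm, a few patients could still shift a table.

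One limit: the SAP is written to protocol v5.0, and the protocol reviewed is v4.0. The collection wording may have changed, but the SAP keeps the IMP-only anchor for TEAEs.

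**What to change.** - **Collection.** Reconcile protocol 3.1, 7.3, 7.4 and Table 1 footnotes a, r and s so that AE and SAE collection runs to 28 days after the last dose of IMP or pembrolizumab, whichever comes later. Section 5.3.3 already uses that anchor.
- **Analysis.** Define the main TEAE summary on the same window in protocol 7.1.1 and 8.4.6 and SAP 10.10.1. Keep the table cut at last IMP dose + 28 days as supplementary.
- **Leave alone.** Keep the Safety Follow-up Visit 28 days after the last IMP dose. Tying it to the later drug would remove the dedicated post-IMP check for patients who stopped IMP for toxicity.

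This changes no dose or stopping rule and takes no position on whether pembrolizumab should continue after an IMP-only stop.

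The cost is protocol wording, one SAP definition, one extra table and some additional AE entry for a few patients. Some late events in the main table will be due to pembrolizumab alone, and the supplementary table separates them. The analysis change can be applied to whatever AEs have been collected.
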